2. STUDY DESIGN

2.1 General Study Design

Study SHP465-308 is a Phase 3, open-label, multicenter, 12-month safety and tolerability study of SHP465 in children (aged 4-12 years, inclusive, at the time of consent was obtained in the antecedent study [SHP465-112 or SHP465-309] or at the time of consent into this study if directly enrolled) with ADHD.

Approximately 80 subjects will be enrolled into this study. Subjects enrolled in this study will be divided into 2 groups based on participation in antecedent studies as follows:

- Subjects in Group A are those who have been rolled over from antecedent studies (SHP465-112 or SHP465-309). These subjects do not need additional screening and washout procedures.
- Subjects in Group B will be directly enrolled subjects who will be required to undergo full screening and washout procedures before first dose.

Antecedent study SHP465-112 is a Phase 1 study in subjects aged 4-5 years who were administered 6.25 mg SHP465. Antecedent study SHP465-309 is a Phase 3 study in subjects aged 6-12 years who were randomized to either 6.25 mg SHP465 or placebo.

For subjects in Group A, the baseline defined in the antecedent study, SHP465-112 or SHP465-309, will serve as the baseline visit (Visit 2) for analyses of this study. For subjects in Group B, a screening visit will precede a washout period. Data will be summarized using the following layouts:

- For full analysis, data will be summarized using the following 5 columns:
 - Antecedent Study:
 - Group A 112 SHP465 6.25mg
 - Group A 309 Placebo
 - Group A 309 SHP465 6.25mg
 - Direct Enrollment: Group B SHP465 6.25mg
 - Total
- For full analysis by-age group summaries, data will be summarized using the following 3 columns:
 - Group A Antecedent Study
 - Group B Direct Enrollment
 - Total

For all subjects in Group A and Group B, SHP465 will be administered as a daily morning dose of 6.25 mg in the treatment of ADHD.

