11.4 Electrocardiogram (ECG)

Electrocardiogram (ECG) data will be summarized by treatment group of the antecedent studies, current treatment (SHP465) for each enrollment type, and overall. ECG results and change from baseline will be summarized at each visit and at the FoTA. If there are multiple assessments for the interpretation at any visit, the worst interpretation will be used in the summary tables. For the interval parameters at post-baseline visits, the first readable result will be used if there are multiple assessments.

For the ECG interval parameters, baseline is defined as the average of all valid ECG measurements as the last assessment obtained prior to the first dose of the investigational product. For the ECG interpretation, baseline will be the ECG with the worst interpretation obtained at the baseline Visit (Visit 2), providing this is prior to the first dose of the investigational product.

PCI criteria will be applied to all ECG data at each visit including any repeat/unscheduled assessments and presented by visit. PCI criteria are defined in [Table 10](#) for Age 4-5 years or if they meet the criteria in [Table 11](#) for Age 6-12 years.

Table 10 Criteria for Potentially Clinically Important ECG Values for Age 4-5 Years

ECG Parameter	Unit	Observed Value		Change from Baseline	
		Lower Limit	Higher Limit	Lower Limit	Higher Limit
ECG Result	-	-	Abnormal (core lab) and Clinically significant from investigator	-	-
Heart Rate	Beats/minute	<55	>130	Decrease >15	Increase >15
PR Interval	msec	-	≥200	-	-
QT Interval	msec	-	≥440	-	≥30 and <60 ≥60
QTcF Interval	msec	-	≥440 and <480 ≥480 and <500 ≥500	-	≥30 and <60 ≥60
QTcB Interval	msec	-	≥440 and <480 ≥480 and <500 ≥500	-	≥30 and <60 ≥60
QRS Interval	msec	-	≥90	-	-
Rhythm	-	-	Any rhythm other than sinus rhythm*	-	-

Age is calculated from the informed consent date from antecedent studies for Group A and from the informed consent date from SHP465-308 for Group B.

Table 11 Criteria for Potentially Clinically Important ECG Values for Age 6-12 Years

ECG Parameter	Outlier Criteria
ECG result	Shift from a normal baseline to an abnormal finding or from an abnormal baseline to a new abnormal finding
Heart rate	≤50 beats/minute* or ≥100 beats/minute*
PR interval (increase)	≥200 msec*
QRS interval	≥120 msec*
QTcF/QTcB	≥450 msec* and <480 msec* ≥480 msec* and <500 msec* ≥ 500msec*
QT/QTc from Baseline	≥30 msec* and <60 msec* ≥60 msec*

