*The NCI has not specified a value, Shire physicians have agreed on values provided.

ECG=electrocardiogram; QTcB=Bazett's corrected QT interval; QTcF=Fridericia's corrected QT interval

Age is calculated from the informed consent date from antecedent studies for Group A and from the informed consent date from SHP465-308 for Group B.

The number and percentage of subjects with post-baseline PCI values will be tabulated. The percentages for the observed value criteria will be calculated relative to the number of subjects with at least 1 post-baseline assessment available per parameter and visit. The percentages for the change from baseline criteria will be calculated relative to the number of subjects with available baseline and at least 1 post-baseline assessment per parameter and visit. The numerator is the total number of subjects with at least 1 PCI post-baseline ECG value.

Additionally, a summary table showing the number and percentage of subjects with the Central Reader's assessment of the ECG result as normal, abnormal or unable to evaluate, and the investigator's assessment of abnormal ECG results as not clinically significant or clinically significant at each visit and at the FoTA will be produced. A shift table showing the change in evaluation from baseline to the FoTA will also be produced.

Listings of ECG data including the central reader's assessment and investigator's interpretation by individual subject will be produced. Separate listings will be produced for subjects with ECG results meeting the PCI criteria. Data from unscheduled visits will be listed, but not summarized.

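### The ECG-result row of the SAP's PCI criteria counts one event at ages 4-5 and another at ages 6-12, so it cannot be compared across columns or pooled

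*SAP*

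**What the plan says.** SAP 11.4 defines PCI ECG values in Table 10 for ages 4-5 and Table 11 for ages 6-12. Both tables have a row for the overall ECG result.

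- Table 10 lists it as an observed-value criterion: "Abnormal (core lab) and Clinically significant from investigator".
- Table 11 defines it as "Shift from a normal baseline to an abnormal finding or from an abnormal baseline to a new abnormal finding".

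The section sets two denominators. Percentages for observed-value criteria are "calculated relative to the number of subjects with at least 1 post-baseline assessment available per parameter and visit". Those for change-from-baseline criteria are "calculated relative to the number of subjects with available baseline and at least 1 post-baseline assessment per parameter and visit".

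ECG data are to be summarised by antecedent-study treatment group, by enrollment type and overall. SAP 2.1 ties the antecedent columns to age: "Antecedent study SHP465-112 is a Phase 1 study in subjects aged 4-5 years", and SHP465-309 enrolled ages 6-12. The footnotes to both tables take age from the antecedent consent date for rollover children, so nobody changes table on a birthday during this study.

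**The concern.** Age can be a reason for different millisecond or heart-rate limits. It does not explain why an abnormal reading needs the investigator's agreement that it is clinically significant at age 5 but not at age 6, and the SAP offers no explanation. The two rules differ in three ways: the significance condition, the comparison with baseline, and whose reading counts (Table 11 does not say).

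Because the antecedent columns are also age columns, the difference carries straight into the reported table. Safety is the primary objective, and at least 40 children aged 4-5 are planned. Someone reading along this row could take a difference in definition for a difference in ECG findings between preschool and older children, and the overall figure would describe neither event.

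**Working it through.** The plan states no figure here, so there is none to reproduce. The check compares the rules, follows them into the columns, and shows how the gap behaves.

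**1. The row side by side**

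| | Table 10, ages 4-5 | Table 11, ages 6-12 |
|---|---|---|
| Abnormal according to | Core lab | Not stated |
| Investigator must rate it clinically significant | Yes | No |
| Must be new against baseline | No | Yes |
| Denominator that follows | Post-baseline ECG only | Baseline and post-baseline ECG |

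**2. Which column uses which rule**

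- SHP465-112 rollovers: Table 10 only.
- SHP465-309 rollovers, both columns: Table 11 only.
- Overall, and Group B where it includes both ages: a sum of the two events.

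**3. Size of the gap**

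Let q be the proportion of children with a new abnormality, taken as equal at all ages, and f the share of them whose abnormality is rated clinically significant. The documents give neither. Ignoring significant abnormalities that persist from baseline (exclusion criterion 13 should make them rare):

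- Expected rate at 6-12 = q. Expected rate at 4-5 = q × f. Ratio of the two = f.
- Assumed q of 5-20% and f of 5-50%: the younger rate runs from 5% × 5% = 0.25% to 20% × 50% = 10%, against 5% to 20%. That is a 2- to 20-fold gap (1/f). At f = 100% there is none.
- Example, q = 10% and f = 10%: 1% against 10%. Among 40 children aged 4-5, 0.4 are expected to be flagged, and the chance that none is flagged is (1 − 0.01)^40 = 67%.
- Overall column in the same example, with 40 children aged 4-5: at the protocol's 145 subjects, (40 × 0.01 + 105 × 0.10)/145 = 7.5%. At the SAP's 80 subjects, (40 × 0.01 + 40 × 0.10)/80 = 5.5%. A common new-abnormality rule gives 10% in both.

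**4. The other rows**

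| Row | Ages 4-5 | Ages 6-12 | Flags more readily |
|---|---|---|---|
| Rhythm | "Any rhythm other than sinus rhythm" | No row | 4-5 |
| QRS | ≥90 msec | ≥120 msec | 4-5 |
| QTcF/QTcB, lowest band | From 440 msec | "≥450 msec* and <480 msec" | 4-5 |
| Absolute QT | ≥440 msec | No row | 4-5 |
| Heart-rate change | More than 15 bpm | No row | 4-5 |
| Heart rate, low | <55 bpm | ≤50 bpm | 4-5 |
| Heart rate, high | >130 bpm | ≥100 bpm | 6-12 |
| PR; QT/QTc change bands | Same | Same | Neither |

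The 6-12 heart-rate limits read "≤50 beats/minute* or ≥100 beats/minute". Identical assumed normal distributions show the direction:

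- QRS with mean 80, SD 10 msec: 1 − Φ((90 − 80)/10) = 15.9% at 4-5 and under 0.01% at 6-12.
- QTc with mean 410, SD 20 msec: 6.7% and 2.3%.
- Heart rate with mean 95, SD 12 bpm against the upper limits: 0.2% and 34%.

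**5. What the rest of SAP 11.4 supplies**

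On one definition for all ages, it plans the central reader's result and the investigator's significance call at each visit and at the final on-treatment assessment (FoTA), a baseline-to-FoTA shift table, and full listings. None of these tables counts new abnormalities against baseline at ages 4-5 other than at FoTA. PCI criteria also take in repeat and unscheduled ECGs, whereas unscheduled data are otherwise listed but not summarised.

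**6. Baseline for the shift rule**

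SAP 11.4 takes the interpretation baseline from Visit 2. Under protocol Table 2, note m, a Group B child has a Visit 2 ECG only if more than 32 days have passed since screening. Read literally, the Table 11 shift has no baseline for other Group B children.

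**The case against.** A reader might infer that these criteria make the youngest children look safer on ECG in general. The documents do not support that. Six of the rows compared above flag ages 4-5 more readily, or exist only for that age, and none of them depends on the investigator's opinion. Only the upper heart-rate limit clearly runs the other way.

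Nor are abnormalities at ages 4-5 hidden. One that is rated not significant still appears in the by-visit reader table, the significance table and the listings.

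Three further points count against a strong reading. SAP 2.1 defines a by-age layout, and if the PCI table used it, each column would carry one definition; the table templates are in a separate document. All analyses are descriptive, and no objective compares age groups. Finally, no near-zero rate at 4-5 can be asserted: the share rated significant is unknown, PCI results are presented by visit, and the study was terminated early, so some children may have had few ECGs.

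These arguments limit the point without removing it. SAP 11.4 itself specifies summaries by antecedent group, enrollment type and overall, and nothing there assigns this row to the by-age layout. The common-definition tables do not replace a count of new abnormalities at any visit.

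**Conclusion.** The ECG-result PCI row is not comparable between ages 4-5 and 6-12. As SAP 11.4 is written, the SHP465-112 and SHP465-309 columns count different events in it, and the overall column mixes them. This follows from the text and needs no assumption.

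The size of the gap does need one. For equal underlying rates, the ratio of younger to older is the share of new abnormalities rated clinically significant, which the documents do not give. The 1% against 10% example only illustrates that relation.

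The conclusion covers this row and does not extend to ECG PCI findings as a whole. It is a limited reporting defect, worth correcting because the correction is cheap.

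**What to change.** Replace the ECG-result row with two rows, both reported for all ages:

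1. Shift to a new abnormal finding against baseline, by the central reader, among children with a baseline and at least one post-baseline ECG.
2. Post-baseline ECG abnormal by the core lab and rated clinically significant by the investigator, among children with at least one post-baseline ECG.

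Apply each denominator identically at all ages. For the interpretation baseline, use the last ECG (or triplicate set) before the first dose in this study. This agrees with the general baseline rule in SAP 11 and gives Group B children without a Visit 2 ECG a baseline.

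At minimum, show the existing row by age group only, footnote its definition, and leave it out of any pooled column.

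The cost is one extra row per table and a small programming change. Protocol 7.2.3.8 already obtains the central reading and the investigator's significance assessment for ECGs, and Table 11 already requires new findings to be identified at ages 6-12. No further data collection is needed beyond what those rules presuppose.

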11.5 Other Safety Variables

Other safety data will be summarized by treatment group of the antecedent studies, current treatment (SHP465) for each enrollment type, and overall using the Safety Set.

11.5.1 Columbia-Suicide Severity Rating Scale (C-SSRS)

The C-SSRS is a semi-structured interview that captures the occurrence, severity, and frequency of suicide-related thoughts and behaviors during the assessment period. The interview includes definitions and suggested questions to solicit the type of information needed to determine if a suicide-related thought or behavior occurred.

The C-SSRS contains two required items pertaining to suicidal ideation, four required items pertaining to suicidal behavior, and one required item pertaining to non-suicidal self-injurious behavior. There are eight additional suicidal ideation items and two additional suicidal behavior items which are completed in cases of positive responses for other items, as well as two items for suicide and suicide behavior present during the interview. Most items are rated on a dichotomous scale (yes or no) or 3- or 5-point Likert scale. In addition, the total number of attempts (including interrupted and aborted attempts) is recorded. In the event of a positive categorical response the interviewer can provide text or narrative that further describes the thought or behavior.

Two versions of C-SSRS, the "Baseline" version and the "Since Last Visit" version, will be used in this study. For subjects in Group A, the "Since Last Visit" version will be completed at all study visits. The scale will be compared with the "Baseline" version from the antecedent study. For subjects in Group B, the "Baseline" version will be administered at the Screening Visit (Visit 1) and the "Since Last Visit" version will be completed for all subjects at all study visits after the Screening Visit (Visit 1).

Positive results from the C-SSRS data will be descriptively summarized for overall during the study and by visit.

A listing of the C-SSRS data will be provided for subjects with a positive response.

11.5.2 Post Sleep Questionnaire (PSQ)

The PSQ is a 7-item questionnaire typically used to assess sleep quality with pharmacologic treatment. The questionnaire collects data on average time to sleep, sleep latency, frequency of interrupted sleep, duration of interrupted sleep, total sleep time and sleep quality over the last week. The PSQ will be completed by the parent/LAR with the subject and the responses will be reviewed by the clinician during the study visit.

The PSQ will be conducted at each visit to the site starting with the baseline visit (Visit 2) and will be completed by the subject's parent/LAR.

The PSQ results will be summarized by visit. Continuous variables, for example, time to go to sleep and time spent awake, will be summarized using number of subjects, mean and standard deviation, median, and minimum and maximum values. Categorical values, for example, quality of sleep, will be summarized using number of subjects and percentages for each category.

11.5.3 Children's Sleep Habit Questionnaire (CSHQ)

The Child's Sleep Habits Questionnaire (CHSQ) consists of 33 items for scoring and several extra items intended to provide administrators with other potentially useful information about respondents. Each scored question except for Watching TV and Riding in car is rated on a 3-point scale:

- occurring "usually" (i.e., 5–7 times within the past week): score = 3
- occurring "sometimes" (i.e., 2–4 times within the past week): score = 2
- occurring "rarely" (i.e., never or 1 time within the past week): score = 1

The following six questions should be reversed in scoring for calculation of subscale score and total sleep disturbance score so that higher score reflects more disturbed sleep behavior: "Goes to bed at same time", "Falls asleep in own bed", "Falls asleep in 20 minutes", "Sleeps the right amount", "Sleeps same amount each day", "Wakes by himself". These six questions are rated on 3-point scale depending on the frequency of occurring:

- "usually" (5– times within the past week): score = 1
- "sometimes" (2– times within the past week): score = 2
- "rarely" (never or 1 time within the past week): score = 3

Questions of Watching TV and Riding in car is rated on a 3-point scale (more than 1 occurrences can apply for each question, highest score contributes as the question score):

- occurring "not sleepy": score = 0
- occurring "very sleepy": score = 1
- occurring "falls asleep": score = 2

The instrument evaluates the child's sleep based on behavior within 8 different subscales:

1. Bedtime resistance (sum of the responses for Goes to bed at same time, Falls asleep in own bed, Falls asleep in other's bed, Needs parent in room to sleep, Struggles at bedtime and Afraid of sleeping alone)
2. Sleep-onset delay (Falls asleep in 20 minutes item)
3. Sleep duration (sum of the responses for Sleeps too little, Sleeps the right amount and Sleeps same amount each day)
4. Sleep anxiety (sum of the responses for Needs parent in room to sleep, Afraid of sleeping in the dark, Afraid of sleeping alone and Trouble sleeping away)
5. Night wakings (sum of the responses for Moves to other's bed in night, Awakes once during night and Awakes more than once)
6. Parasomnias (sum of the responses for Wets the bed at night, Talks during sleep, Restless and moves a lot, Sleepwalks, Grinds teeth during sleep, Awakens screaming, sweating and Alarmed by scary dream)
7. Sleep-disordered breathing (sum of the responses for Snores loudly, Stops breathing and Snorts and gasps)
8. Daytime sleepiness (sum of the responses for Wakes by himself, Wakes up in negative mood, Others wake child, Hard time getting out of bed, Takes long time to be alert, Seems tired, Watching TV and Riding in car)

Total sleep disturbance score is sum of the 8 subscale scores minus Needs parent in room to sleep and Afraid of sleeping alone (as Needs parent in room to sleep and Afraid of sleeping alone are included in two subscales (1 and 4) and need to be included once). Missing data will not be imputed.

Total sleep disturbance score, each subscale and each individual item will be summarized using descriptive statistics (n, mean, SD, minimum, median, and maximum) at each visit (and Visit 6/ET) by treatment group of the antecedent studies, current treatment (SHP465) for each enrollment type, and overall . All CSHQ data will be listed for the Safety Set.

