#### **7.2.3.10 Children's Sleep Habits Questionnaire**

The CSHQ is a tool designed to screen for the most common sleep problems in children and consists of 33 items for scoring and several extra items intended to provide administrators with other potentially useful information about respondents. The instrument evaluates the child's

sleep based on behavior within 8 different subscales: bedtime resistance, sleep-onset delay, sleep duration, sleep anxiety, night wakings, parasomnias, sleep-disordered breathing, and daytime sleepiness.

The CSHQ will be conducted at each visit to the site starting with the baseline visit (Visit 2) and will be completed by the subject's parent/LAR.

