## 9.9 Safety Analyses

Safety assessments include the occurrence of TEAEs and evaluations of blood pressure, pulse, height, weight, BMI, results of clinical laboratory evaluations and ECG, sleep questionnaires (PSQ and CSHQ), and C-SSRS.

The safety set will be used to report the safety data. Safety analyses will be presented by treatment group of the antecedent studies and overall.

Adverse events will be coded using the Medical Dictionary for Regulatory Activities. Treatment emergent AEs are defined as AEs that started or deteriorated on or after the date of the first dose of investigational product, and no later than 3 days following the last dose of investigational product. The number of events, incidence, and percentage of TEAEs will be calculated overall, by system organ class, by preferred term, and by treatment group. Treatment emergent AEs will be further summarized by severity and relationship to investigational product. Adverse events related to investigational product, AEs leading to withdrawal, SAEs, and deaths will be similarly summarized/listed.

Clinical laboratory tests, vital signs, and ECG findings will be summarized by visit. Potentially clinically important findings will also be summarized or listed.

The PSQ and CSHQ will be summarized using appropriate descriptive statistics at each visit.

The C-SSRS results will be summarized and listings of the C-SSRS data will be provided for subjects with a positive response.

In addition, the safety data on TEAEs will also be descriptively summarized by treatment within each age (4-5 years and 6-12 years), sex, race (white and non-white), and ethnicity subgroup.

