3. OBJECTIVES

3.1 Primary Objective

The primary objective is to evaluate the long-term safety and tolerability of SHP465 at 6.25mg administered as a daily morning dose in children aged 4-12 years (inclusive at the time of consent) diagnosed with Attention-deficit/Hyperactivity Disorder (ADHD).

The evaluation of safety and tolerability will be based on the occurrence of treatment-emergent adverse events (TEAEs), evaluation of vital signs (systolic and diastolic blood pressure and pulse), weight, height, body mass index (BMI); clinical laboratory and electrocardiogram (ECG) results; sleep assessment (Post Sleep Questionnaire [PSQ], and Children's Sleep Habits Questionnaire [CSHQ]); and responses to the Columbia-Suicide Severity Rating Scale (C-SSRS).

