11. SAFETY ANALYSES

Safety data will be analyzed for the Safety Set by treatment group of the antecedent studies, current treatment (SHP465) for each enrollment type, and overall. Safety endpoints include the occurrence of TEAEs, vital signs (systolic and diastolic blood pressure, and pulse), height, weight, body mass index (BMI); clinical laboratory and ECG results, C-SSRS, and sleep questionnaires (PSQ and CSHQ). For each safety endpoint, the last value collected before the first dose of investigational product in this study will be used as baseline for all analyses of that safety endpoint. Except for adverse event data, only post-baseline assessments from Visit 2 (Week 0) up to Visit 16 (Month 12) that were collected on or 2 days after the last dose of investigational product will be analyzed. A Final on-Treatment Assessment (FoTA) will be defined as the last valid assessment obtained after Baseline and whilst on investigational product (on or before 2 days after the last dose date).

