11.2 Clinical Laboratory Variables

Descriptive statistics for clinical laboratory values (in SI units) and changes from Baseline to Visit 16/ET as well as shift tables from Baseline to Visit 16/ET for quantitative variables will be presented by treatment group of the antecedent studies, current treatment (SHP465) for each enrollment type, and overall for the following clinical laboratory variables:

Biochemistry and Endocrinology

Total cholesterol	Calcium
Aspartate aminotransferase	Urate
Phosphorus	Blood urea nitrogen
Alanine aminotransferase	Total bilirubin
Sodium	Creatinine
Alkaline phosphatase	Glucose
Potassium	Albumin
Gamma-glutamyl transferase	Total protein
Thyroid-stimulating hormone	Lactate dehydrogenase
Thyroxine, Free	

Hematology

Hemoglobin	Neutrophils
Hematocrit	Lymphocytes
Red blood cells	Monocytes
Platelet count	Eosinophils
White blood cell count – total and differential	Basophils
Mean corpuscular hemoglobin	Neutrophils Band Forms
Mean corpuscular hemoglobin concentration	Mean corpuscular volume

Urinalysis

Glucose	pH
Specific gravity	Urobilinogen
Blood	Color
Ketones	Leukocyte esterase
Protein	Nitrite
Bilirubin	

Microscopic examination will be conducted if protein and/or blood is/are detected during urinalysis. At a minimum the microscopic examination will consist of red blood cells, white blood cells, casts, and bacteria.

Clinical laboratory test values are potentially clinically important (PCI) if they meet either the low or high PCI criteria. The PCI criteria are listed in [Table 4](#) for subjects aged 4-5 years and [Table 5](#) for subjects aged 6-12 years. The number and percentage of subjects with post-baseline PCI values will be tabulated. The percentages will be calculated relative to the number of subjects with available baseline values and at least 1 post-baseline assessment. The numerator is the total number of subjects with at least 1 post-baseline PCI value. A supportive listing of subjects with post-baseline PCI values will be provided including the subject number, baseline, and post-baseline values.

Table 4 Criteria for Potentially Clinically Important Laboratory Tests for Subjects Aged 4-5 Years

Parameter	SI Unit	Lower Limit	Higher Limit
Biochemistry			
Albumin	g/L	< 30g/L	-
Aspartate transaminase (AST)	-	-	>3 x ULN
Alanine transaminase (ALT)	-	-	> 3 x ULN
Alkaline phosphatase			>2.5 x ULN
Blood urea nitrogen	mmol/L	-	> 10.7mmol/L or > 2.5 x ULN
Calcium	mmol/L	< 2	> 2.9
Total cholesterol	mmol/L	-	> 7.8

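### PSQ and CSHQ, part of the primary safety objective, are summarized only as values by visit, with no paired change from the SAP 11 baseline and no final on-treatment row

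*SAP*

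**What the plan says.** SAP 3.1 counts "sleep assessment (Post Sleep Questionnaire [PSQ" and the CSHQ among the measures on which the primary safety objective rests. SAP 11 lists both as safety endpoints. It says that the last value before the first dose in this study "will be used as baseline for all analyses of that safety endpoint", and it defines FoTA as the last valid post-baseline assessment on treatment, with two days allowed after the last dose.

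The sleep sections then use neither device for a change summary:

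- SAP 11.5.2: "The PSQ results will be summarized by visit", as descriptive statistics for continuous items and counts with percentages for categorical ones.
- SAP 11.5.3, for the CSHQ total, subscales and items: "each individual item will be summarized using descriptive statistics (n, mean, SD, minimum, median, and maximum) at each visit (and Visit 6/ET".

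The protocol asks for no more. Protocol 9.9 states: "The PSQ and CSHQ will be summarized using appropriate descriptive statistics at each visit". SAP 13 plans no further analyses.

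**The concern.** Insomnia is a known effect of this product (Protocol 1.2) and an event of clinical interest in SAP 11.1.1. The natural question for a 12-month open-label safety study is whether a child's sleep became better or worse on treatment, and what it was like when treatment ended. A table of visit means answers neither question directly.

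The set of children contributing to each row will change. Some will leave early, and the sponsor stopped the study (SAP 1), which cuts follow-up according to entry date. Leaving can also be linked to sleep. Protocol 7.2.3.12 tells the investigator to manage clinically significant insomnia first and to consider stopping treatment if needed. If children with worsening sleep leave, later means can look better although no remaining child has improved.

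**Working it through.** The plan gives no figure to reproduce, so the check is a comparison of sections followed by what the planned tables can and cannot show.

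**1. How the SAP treats its safety measures**

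| Measure | Change from baseline | Last-status row |
|---|---|---|
| Vital signs (11.3) | each post-baseline visit | FoTA |
| ECG (11.4) | each visit | FoTA |
| Laboratory (11.2) | "changes from Baseline to Visit 16/ET as well as shift tables from Baseline to Visit 16/ET" | Visit 16/ET |
| C-SSRS (11.5.1) | positive results overall and by visit | none |
| PSQ (11.5.2) | none | none |
| CSHQ (11.5.3) | none | unclear (see step 3) |

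Protocol 9.9 asks only for by-visit summaries of laboratory tests, vital signs and ECG as well. The SAP went further for those three and did not for sleep. ADHD-RS-5, a secondary measure, also gets change from baseline at each visit (SAP 10.2.1).

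**2. What a difference of visit means contains**

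Let S0 be the children with a baseline score and Sv those with both a baseline and a visit-v score. Assume that everyone scored at visit v has a baseline. Write M0 and Mv for mean scores at baseline and visit v, and Dv for mean within-child change. Then

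Mv(Sv) − M0(S0) = Dv(Sv) + [M0(Sv) − M0(S0)].

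The planned tables give the left side. The within-child term Dv(Sv) cannot be separated from the bracket, which reflects who is still contributing. The two sides agree without the bracket only if the contributing children have the same mean baseline as all children. The spread of change is not recoverable either: Var(change) = Var(baseline) + Var(visit) − 2·Cov, and no covariance is reported.

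Dv(Sv) is still an average over children who remain. Reporting change by visit removes the bracket but does not bring back those who left. FoTA does, for every child with a baseline and at least one valid on-treatment assessment afterwards.

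**3. Whether a last-status row already exists**

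Visit 6 is Month 2 in both schedules, and ET is paired with Visit 16, so the CSHQ wording looks like a slip for Visit 16/ET. Correcting it does not produce FoTA. SAP 18.3 assigns an early-termination assessment to the nominal visit after the last one completed and exempts only laboratory data. A last completed visit of 2 to 15 therefore gives a row from 3 to 16, which is 16 − 3 + 1 = 14 possible rows. Under that rule the Visit 16 row holds completers and children who left after Visit 15. SAP 18.4 says which repeat counts as the final on-treatment assessment but adds no sleep summary.

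**4. Whether the baseline is available**

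For the CSHQ, "The CSHQ will be conducted at each visit to the site starting with the baseline visit (Visit 2"; Protocol 7.2.3.9 says the same of PSQ. Dosing starts the morning after Visit 2 (Protocol 6.2.3), so a pre-dose value in this study is scheduled for everyone.

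For Group A, Visit 2 falls on the day of the final on-site visit of the antecedent study (Protocol 7.1.1.3). By SAP 2.1, children from 112 received SHP465 6.25 mg, and those from 309 received SHP465 6.25 mg or placebo. The 112 and 309-active rollovers therefore have a baseline after drug exposure; 309-placebo rollovers and Group B do not.

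SAP 2.1 also says that for Group A the antecedent-study baseline "will serve as the baseline visit (Visit 2) for analyses of this study", which competes with SAP 11.

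**The case against.** The strongest reply is that nothing is broken. The protocol asks for descriptive statistics at each visit and the SAP supplies them. SAP 11 defines baseline and FoTA without requiring every endpoint to use them; C-SSRS uses no FoTA, and laboratory data use Visit 16/ET. Because both scales start at Visit 2, a baseline row of values can appear. Insomnia events are summarized by onset, duration, severity, outcome and month (SAP 11.1.1), and CSHQ data are listed (SAP 11.5.3). The table shells are in a separate document (SAP 20) that was not available.

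Most of this stands. A reader might infer a breach of the protocol, or a baseline that is ignored altogether; the documents support neither. What is missing is paired change and FoTA. Adverse event counts are not scale scores, and a listing from which change could be derived is not a summary of change.

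Two further objections limit the argument. First, a leaver's early-termination value is not lost: if taken within the on-treatment limit it enters the next nominal row. The difficulty is that such values are spread out, so no row collects last status. Second, change by visit is as much a summary of remaining children as values by visit. It is tempting to present it as the cure for sleep-related dropout, but only FoTA addresses that. The protocol's link between insomnia and stopping treatment is conditional, and no dropout rate is given.

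**Conclusion.** The gap is real and worth closing. For two components of the primary safety objective, the SAP text plans neither a within-child comparison nor a last on-treatment summary, although it defines both tools and applies them to vital signs and ECG. The plan is consistent with Protocol 9.9.

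No size can be given in PSQ or CSHQ units: the documents contain no scores, no variances and no discontinuation rates. A reader might look for a magnitude elsewhere. With in-window visits, SAP 18.3 can label an early-termination value up to 30 + 5 − 1 = 34 days later than it occurred, and the termination decision of 14 Dec 2018 limited who could reach Month 12. The first describes a SAP-wide labelling rule and the second the length of follow-up. Neither measures the effect of omitting change and FoTA for sleep.

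The conclusion assumes that the unseen table shells follow the SAP text. Without a concurrent control arm, the added summaries would describe change and would not attribute it to SHP465.

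**What to change.** 1. **SAP 11.5.3:** add change from baseline in the CSHQ total and subscale scores at each visit, and both value and change at FoTA.
2. **SAP 11.5.2:** add the same for the continuous PSQ items.
3. **Both sections:** state that baseline is the SAP 11 safety baseline (last value before first dose in this study), not the antecedent-study baseline named for Group A in SAP 2.1.
4. **Presentation:** show change in the existing antecedent-group columns. Footnote that 112 and 309-active rollovers have a drug-exposed baseline, so the Total column mixes on-drug and pre-drug baselines. A footnote does not remove that mixture, so the separate columns should carry the interpretation.
5. **Editorial:** correct Visit 6/ET to Visit 16/ET.

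A count of children with a CSHQ total of 41 or more could be added as a descriptive extra. It is optional, and it would not count children meeting the two-consecutive-week example in Protocol 7.2.3.12.

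The cost is extra table rows, a baseline sentence, a footnote and a typing correction. No new assessment or protocol amendment is needed. The documents do not say whether the database was locked; if it was, the rows can still be produced and labelled post hoc.
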